## 11.3.1.16 Procedures in case of pregnancy

In case of pregnancy or suspicion of possible pregnancy of any female partners of male subjects, the outcome of all pregnancies (spontaneous miscarriage, elective termination, normal birth or congenital abnormality) must be followed up and documented even after the end of the subject's trial participation. Pregnancy itself is not regarded as an AE unless there is a suspicion that the IMP may have interfered with the effectiveness of the contraceptive medication.

All events of congenital abnormalities/birth defects are SAEs. Spontaneous miscarriages should also be reported and handled as AEs. All outcomes of pregnancy must be reported to the Sponsor and the Principal Investigator on the pregnancy outcomes report form.

## 11.3.1.17 Treatment of overdose

An overdose is a dose in excess of the dose specified for each cohort in this CTP.

Over-dosing is not likely to occur in this trial since all IMP will be administered by site personnel under medical surveillance. In cases of accidental overdose, standard supportive measures should be adopted as required.

An overdose should be documented as follows:

- An overdose with associated AE is recorded as the AE diagnosis/symptoms in the AE Log of the eCRF.
- An overdose without associated symptoms is reported in the subject's medical records.

In addition, any overdose will be recorded as a protocol deviation.

No known antidote is available.

#### 11.3.2 *Electrocardiogram*

Single 12-lead ECG will be recorded in supine position after 10 minutes of rest using an ECG machine. Heart rate (HR) and PR, QRS, QT and QTcF intervals will be recorded.

Safety ECGs will be reviewed and interpreted on-site by the Investigator.

Any abnormalities will be specified and documented as clinically significant or not clinically significant. Abnormal post-dose findings assessed by the Investigator as clinically significant will be reported as AEs.

For timing of assessments, refer to Table 8.1-1to Table 8.1-5.

## 11.3.3 Telemetry

Ambulatory ECG telemetry will be used for cardiac surveillance up to 24 hours after IMP administration in Part A (SAD).

Telemetry will be reviewed on-site by the Investigator and judged as normal, abnormal not clinically significant or abnormal, clinically significant. If judged as abnormal, clinically significant, a print-out will be saved for documentation. Abnormal post-dose findings assessed by the Investigator as clinically significant will be reported as AEs.

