# Effects on the cardiovascular system

Cardiovascular effects of C106 treatment were observed in Beagle dogs. The main findings were increased blood pressure and electrocardiogram (ECG) aberrations. Increases in systolic and diastolic arterial pressure were observed at doses of 10 to 40 mg/kg in a single dose telemetry study. The heart rate showed a slight, yet statistically significant, increase between 45 and 180 minutes after administration. The ECG intervals RR and QT were decreased at all doses tested (10-40 mg/kg), and these changes were compatible with the increase in heart rate. In addition, second degree atrioventricular (AV) block was observed as repeated incidences at different time-points following administration of 10 to 40 mg/kg.

No toxicologically relevant changes in body temperature were observed following treatment with C106 at any dose tested.

In addition, upon evaluating binding affinity to the human potassium channel hERG, C106 did not show any significant binding at 1  $\mu$ M.

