# 11.3 Assessments related to primary endpoints

## 11.3.1 Adverse events

The Principal Investigator is responsible for ensuring that all medical staff involved in the trial is familiar with the content of this section and the content of the CTC standard operating procedures (SOPs) regarding emergencies and FIH studies.

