## 11.3.4 Vital signs

At visits and time points outlined in Table 8.1-1 and Table 8.1-2 (Part I) and in Table 8.1-3, Table 8.1-4 and Table 8.1-5 (Part II), systolic and diastolic blood pressure (BP) and pulse will be measured in supine position after 10 minutes of rest. Respiratory rate will be assessed. Body temperature will be measured using a digital thermometer on Day -1 of each part.

Any vital signs outside the normal ranges will be judged as not clinically significant or clinically significant. The assessment will be recorded in the eCRF. Abnormal post-dose findings assessed by the Investigator as clinically significant will be reported as AEs.

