#### 17.5.2 *12-lead ECG*

All ECGs will be categorised as" normal", "abnormal", "not clinically significant", or "abnormal, clinically significant" (as judged by the Investigator) and summarised by treatment and cohort using frequency tables. Changes over time will be presented using shift tables, if considered appropriate. All data will be listed by part, cohort, treatment, and subject.

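### AV block or pauses seen only on Part A telemetry and judged not clinically significant have no stated record and no planned comparison with placebo

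*Combined protocol and SAP*

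**What the plan says.** Section 6.1.5 reports that in the dog telemetry study "second degree atrioventricular (AV) block was observed as repeated incidences at different time-points". Section 6.1.6 names second-degree AV block as the main toxicological finding in the dog. Section 6.3 assumes, by analogy with C21, that the cardiovascular effects in dogs do not carry over to humans. It then points to frequent blood pressure and ECG monitoring, including telemetry in the single-dose part.

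Section 11.3.3 stands under the heading "Assessments related to primary endpoints". It gives three steps:

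- **Classification:** "Telemetry will be reviewed on-site by the Investigator and judged as normal, abnormal not clinically significant or abnormal, clinically significant".
- **Retention:** "If judged as abnormal, clinically significant, a print-out will be saved for documentation".
- **Reporting:** "Abnormal post-dose findings assessed by the Investigator as clinically significant will be reported as AEs".

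No step is stated for an abnormality judged not clinically significant.

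Section 17.5 covers AEs, 12-lead ECG, vital signs, laboratory data and physical examination. The 12-lead ECG categories are "summarised by treatment and cohort using frequency tables" (17.5.2). Telemetry is not mentioned in Section 17.

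**The concern.** Telemetry is the continuous cardiac monitoring that the plan puts forward for a finding that was intermittent in dogs. Brief, asymptomatic second-degree AV block in a healthy volunteer could well be judged not clinically significant. Under 11.3.3 as written, such an episode need not be described, entered or kept.

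A single episode of this kind may mean little. A higher count on C106 than on placebo, or a count rising with dose, would mean more, and it can be seen only if episodes are recorded irrespective of the judgement. Section 8.2 gives this as the reason for having a placebo group: to show how often changes occur without active treatment. Without the record, the report could state that no AV-block signal was seen when non-significant episodes on telemetry had not been counted.

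Exposure is also rising. Section 8.3.2 reports a 13.2-fold increase in mean Cmax from 60 to 180 mg, with 240 and 300 mg planned next.

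**Working it through.** **1. How each safety assessment treats an abnormality judged not clinically significant**

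| Assessment | Stated recording | Summary in 17.5 |
|---|---|---|
| 12-lead ECG (11.3.2) | Any abnormality specified and documented, significant or not | 17.5.2 |
| Vital signs (11.3.4) | Judged either way; "The assessment will be recorded in the eCRF" | 17.5.3 |
| Laboratory (11.3.5) | Judged either way, with eCRF entry | 17.5.4 |
| Physical examination (11.3.6) | Any abnormality specified and documented, significant or not | 17.5.5 |
| Telemetry (11.3.3) | None stated | None |

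Telemetry is the only one of the five without a stated step. The general rule for categorical data in 17.1 could at most tabulate the three-level judgement, if that is recorded. It would not count AV block.

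**2. Denominators**

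Section 9.3 gives six Part A cohorts of 6 C106 and 2 placebo: 6 × (6 + 2) = 48, as stated, that is 36 on C106 and 12 on placebo.

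- Fasted cohorts with stored Holter (all but A1): 5 × 6 = 30 and 5 × 2 = 10.
- Cohorts not yet run when this version was written (A5 and A6): 2 × 6 = 12 and 2 × 2 = 4.

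**3. What the scheduled 12-lead ECGs can show (illustration)**

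Table 8.1-2 has six post-dose ECGs up to 24 h: 40 min, 2, 4, 6, 10 and 24 h. Assuming 10 s each (the documents give no duration), 6 × 10 = 60 s, and 60 / 86,400 = 0.07% of the telemetry period.

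If block is present for a fraction f of the time, and the six times are treated as independent, the chance that at least one ECG shows it is 1 − (1 − f)^6:

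| Assumed f | Chance |
|---|---|
| 0.1% | 0.6% |
| 1% | 5.9% |
| 5% | 26.5% |

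**4. How the judgement drives what is reported (illustration)**

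Suppose 10% of C106 subjects had AV block on telemetry: 36 × 0.10 = 3.6 expected. If 0%, 25%, 50% or 100% of these were judged clinically significant, the AE tables would show 0, 0.9, 1.8 or 3.6. The reported count then depends on the judgement as much as on the underlying rate.

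**5. What a table could and could not establish**

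With zero events in n subjects, the one-sided 95% upper limit is 1 − 0.05^(1/n):

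| n | Group | Upper limit |
|---|---|---|
| 36 | all C106 | 8.0% |
| 12 | all placebo, or C106 in A5–A6 | 22.1% |
| 6 | one dose | 39.3% |
| 4 | placebo in A5–A6 | 52.7% |

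Against 0/12 on placebo, at least 10/36 on C106 would be needed for a two-sided Fisher p below 0.05 (p = 0.048). The table is therefore descriptive.

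**The case against.** A reader might infer that AV block is not compared with placebo at all, or that a primary endpoint goes unanalysed. The documents support neither reading.

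- **AE route.** Clinically significant telemetry findings become AEs, and 17.5.1 tabulates AEs by part, cohort and treatment. The AE definition covers any unfavourable sign, and Grade 1 includes asymptomatic observations, so an investigator may report silent AV block as an AE. This stands for events judged significant. For the rest, reporting is possible but not required, because 11.3.3 ties it to clinical significance.
- **12-lead ECG.** Block present at a scheduled ECG enters the 17.5.2 tables. The ECG times are also not arbitrary: the 40-minute recording was placed near the assumed Cmax, so the independence assumption in the illustration may understate detection. The 0.07% is a share of time covered, not a detection loss.
- **Endpoint status.** Telemetry sits under the primary-endpoint heading, but Table 7.1-1 does not map it to an endpoint, and 11.3.3 describes it as surveillance. It should not be called a primary endpoint.
- **Holter.** A 25-hour continuous recording is stored in fasted cohorts except A1, so the underlying signal is not wholly lost there. However, 17.7 keeps these data out of the trial report and commits to no analysis. Cohort A1 and the fed period have none.
- **Silence on recording.** That the judgement is not entered in the eCRF is inferred from silence. Section 11.1 requires all data from scheduled assessments to be provided, although it names no telemetry variable.
- **Separate SAP.** Section 17 gives principal features and defers detail to a SAP whose text is not in the combined document. A SAP could add a table; it could not restore episodes that were never recorded.
- **Completed cohorts.** A1 to A4 are complete. If strips were not kept there, pooling placebo across cohorts with different ascertainment would mislead. This stands, and the fix allows for it.

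**Conclusion.** The concern holds in a limited form. In Part A, second- or third-degree AV block or a pause seen only on telemetry and judged not clinically significant has no stated recording and no planned comparison with placebo. This matters because telemetry is offered as a safeguard for the AV block seen in dogs, and because the other four safety assessments each state what happens to a non-significant abnormality.

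The gap touches up to 36 C106 and 12 placebo subjects. The number of episodes lost cannot be derived: it depends on the true rate and on the share judged non-significant, neither of which the documents give. The coverage and capture figures are illustrations that rest on 10 s per ECG and independent times. The conclusion rests on the wording of 11.3.3 and 17.5 and does not need them. Even complete counts would be descriptive at this sample size. The change should be made, but the trial's main safety analysis does not fail without it.

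**What to change.** 1. **Section 11.3.3:** for each subject, record in the eCRF the three-level judgement and every second- or third-degree AV block or pause, with onset and duration, whatever its judged clinical significance. Keep the strip. AE reporting can stay as it is.
2. **Section 17.5.2 (and the SAP):** add a descriptive table of subjects with at least one such episode, by dose and pooled placebo. Restrict it to, or flag, the cohorts and periods with complete ascertainment, so that pooled placebo is compared on the same footing as C106.
3. **Completed cohorts A1 to A4:** use retained source where it exists. Otherwise state in the report that non-significant episodes were not captured. If nothing was kept, full counts would come from A5 and A6 only (12 C106, 4 placebo).

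The cost is a small amount of data entry on a review already being done, and one table. It needs no new subjects or procedures.

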## 11.3.4 Vital signs

At visits and time points outlined in Table 8.1-1 and Table 8.1-2 (Part I) and in Table 8.1-3, Table 8.1-4 and Table 8.1-5 (Part II), systolic and diastolic blood pressure (BP) and pulse will be measured in supine position after 10 minutes of rest. Respiratory rate will be assessed. Body temperature will be measured using a digital thermometer on Day -1 of each part.

Any vital signs outside the normal ranges will be judged as not clinically significant or clinically significant. The assessment will be recorded in the eCRF. Abnormal post-dose findings assessed by the Investigator as clinically significant will be reported as AEs.

## 11.3.5 Laboratory safety assessments

Blood samples for analysis of clinical chemistry, haematology, and coagulation parameters will be collected through venepuncture or an indwelling venous catheter and sent to the certified clinical chemistry laboratory at Uppsala University Hospital and analysed by routine analytical methods.

Urinalysis will be performed at the research clinic using dipsticks. The assessments will be performed at visits specified in (Table 8.1-1 for Part A and Table 8.1-3 for Part B). In addition, urine sampling for analysis of the albumin/creatinine ratio will be performed at all visits where blood sampling for safety laboratory analysis is planned.

The safety laboratory parameters are defined in Table 11.3-1 and will be assessed at timepoints detailed in (Table 8.1-2 for Part A and Table 8.1-4 and Table 8.1-5 for Part B).

Any lab values outside the normal ranges will be judged as not clinically significant or clinically significant. The assessment will be recorded in the eCRF. Abnormal post-dose findings assessed by the Investigator as clinically significant will be reported as AEs.

Category	Parameter
Clinical chemistry	Alanine aminotransferase (ALT)
	Albumin
	Aldosterone
	Alkaline phosphatase (ALP)
	Aspartate aminotransferase (AST)
	Bilirubin (total and conjugated)
	Calcium
	C-reactive protein (CRP)
	Creatinine (eGFR included)

Table 11.3-1 Safety laboratory parameters

Category	Parameter			
	Glucose			
	Phosphate			
	Potassium			
	Sodium			
	Urea (nitrogen)			
Haematology	Haematocrit			
	Haemoglobin (Hb)			
	Platelet count			
	Red blood cell (RBC) count			
	White blood cell (WBC) count with differential count			
Coagulation	Activated Partial Thromboplastin Time (APTT)			
	Prothrombin Complex International Normalised Ratio (PK[INR])			
Urinalysis (dipstick)	Erythrocytes			
	Glucose			
	Ketones			
	Leucocytes			
	Nitrite			
	pH			
	Protein			
	Specific gravity			
	Urobilinogen			
Urinalysis (safety urine sample)	Albumin/creatinine ratio			
FSH-test (at screening, postmenopausal females, questionable cases only)	Follicle stimulating hormone (FSH)			

#### 11.3.6 *Physical examination*

A complete physical examination will include assessments of the head, eyes, ears, nose, throat, skin, neurological, lungs, cardiovascular, and abdomen.

Any abnormalities will be specified and documented as clinically significant or not clinically significant. Abnormal post-dose findings assessed by the Investigator as clinically significant will be reported as AEs.

#### 11.4 Assessments related to secondary endpoints

#### 11.4.1 *Pharmacokinetic blood sampling and analysis*

Venous blood samples (approximately 5 mL) for the determination of plasma concentrations of C106 after administration of the IMP, will be collected through an indwelling venous catheter at the pre-specified time-points Table 8.1-2 for Part A and Table 8.1-4 and

Table 8.1-5 for Part B). Actual time for blood PK sampling must not deviate more than  $\pm 10\%$  from the planned time except as detailed below.

Pre-dose sampling before the first dose in any Part, may be performed within 60 minutes prior to dosing.

The 24-hour and 48-hour samples in Part A should be taken within  $\pm 2$  hours of the planned sampling time point.

Pre-morning dose sampling on Days 2 to 8 in Part B (MAD) must be performed immediately (within 5 minutes) before dosing.

The date and time of collection of each sample will be recorded in the eCRF.

Samples for determination of plasma concentrations of C106, will be analysed by Lablytica Life Science AB, Uppsala by means of a validated bioanalytical method. The details of the analytical method used will be described in a separate bioanalytical report.

Details on sample collection and handling will be provided in a separate laboratory manual.

#### 11.4.2 Urine sampling for analysis of C106

Urine collection for the determination of C106 will be performed in Part A and in Part B (Day 1 and Day 8). In Part A, urine will be collected at visits and time intervals presented in Table 8.1-2. In Part B, urine will be collected at visits and time intervals presented in Table 8.1-4 and Table 8.1-5.

The volume of urine will be determined by total weight and documented in the eCRF. The date and time interval of each collection (start and stop time) will be recorded in the eCRF.

Three urine aliquots (5 mL) from each collection interval and pre-dose samples will be transferred to pre-labelled polypropylene cryotubes and will thereafter immediately be frozen at  $-70^{\circ}$ C until analysed.

Samples for determination of urine concentrations of C106, will be analysed by Lablytica Life Science AB, Uppsala by means of a qualified bioanalytical method. The details of the analytical method used will be described in a separate bioanalytical report.

Details on sample collection and handling will be provided in a separate laboratory manual.

#### 11.5 Assessments related to exploratory endpoints

#### 11.5.1 Metabolite-In-Safety Testing

Blood sampling for future analysis of C106 metabolites will be performed at steady state in Part B (MAD), *i.e.*, from Day 8. The collection of these samples is described in Section 11.4.1. The same samples constitute an aliquot of separated plasma (750  $\mu$ L) generated from each PK sample. Metabolite sampling will be performed at visits presented in Table 8.1-4 and Table 8.1-5.

Details on sample collection and handling will be provided in a separate laboratory manual.

#### 11.5.2 Profile of excreted metabolites in the urine

Urine sampling (an aliquot of 5 mL urine taken from the PK urine samples) for future analysis of excreted C106 metabolites in the urine will be performed at steady state in Part B (MAD),

#### CONFIDENTIAL

*i.e.*, Day 8. The collection and handling of these samples are described in section 11.4.2 at visits presented in Table 8.1-3.

Details on sample collection and handling will be provided in a separate laboratory manual.

## 11.5.3 Cardiodynamic ECG

Twelve (12)-lead ECGs will be extracted from continuous recordings prior to and serially after dosing at time points presented in the schedule of events for Part A of the trial (Table 8.1-3). Continuous ECG recordings will be performed for 25 hours, starting 1 hour prior to dose administration and baseline ECGs will be extracted at 3 time points before dosing (-45, -30 and -15 minutes). Subjects will be supinely resting for at least 15 minutes prior to each time point for PK sampling.

The 12-lead Holter and ECG equipment will be supplied and supported by Clario. All ECG data will be collected using a Global Instrumentation (Manlius, NY, USA) M12R ECG continuous 12 lead digital recorder. The continuous 12-lead digital ECG data will be stored onto SD memory cards. ECGs to be used in the analyses will be selected by pre-determined time points 5 minutes before each PK sample is drawn as defined in the schedule of events (Table 8.1-3) and may be read centrally by Clario.

If a decision is made to analyse data at the Clario core laboratory, a specific analysis protocol will be developed in accordance with accepted standards for EPQT.

#### 11.5.4 Pharmacodynamic assessment (Part B, cohort B4)

[figure not shown]
The PD effect on endothelial function will be assessed by EndoPAT at visits and time points specified in the schedule of events for Part B of the trial (Table 8.1-3 and Table 8.1-4) according to the manufacturer's instructions. The EndoPAT assessments should be done at approximately the same time of the day on both occasions.

The EndoPAT assessment will be conducted in a quiet and relaxed atmosphere. Before initiating the assessment, the subject will be supine for at least 15 minutes. The subjects will be instructed to remain as still as possible during the assessment period. EndoPAT bio sensors will be placed on the subjects right and left index fingers. If this finger is unsuitable (e.g., finger is cut or injured), a different finger may be used as long as the same finger is used on both hands. The same finger should preferably be used at both assessments. A cuff will be placed on the nondominant upper arm for occlusion of the brachial artery.

Each recording will consist of a 5-minute baseline assessment, a 5-minute occlusion assessment, and 5-minute post-occlusion assessment. During the post-occlusion period, blood flow is restored causing an endothelium-dependent vasodilation.

The EndoPAT software, provided with the device, will calculate the RHI and AI scores using a computerised automated algorithm as outlined below. The results will be recorded in the eCRF.

• RHI score: post-to-pre occlusion pulse amplitude tonometry signal ratio in the occluded arm relative to the same ratio in the control arm, and corrected for baseline vascular tone. RHI is a measure of endothelial function.

• AI: calculated from pulse amplitude tonometry pulses at the baseline period. AI is a measurement of vascular stiffness and reflects the structural nature and basal tonus of the vessel.

[figure not shown]
The time points of the initiation and completion of the EndoPAT assessment, the arm occluded, the fingers assessed and any significant deviations from the instructions for use will be recorded in the eCRF.

## **11.6** Appropriateness of measurements

The stopping rules for dose escalation used (see Section 8.3.4) follows the recommendations and grading system of CTCAE v5.0 [40] but also take into account the recommendations published by Sibille et al 2010 [41], which is an adaptation to FIH studies of the grading systems previously proposed by NCI [1], WHO [42], NIH [43] and FDA [44].

EndoPAT is an FDA-cleared, non-invasive device commonly used to assess endothelial function.

All other methods used for safety assessments are commonly used in standard medical care and in Phase 1 clinical trials. Non-compartmental analysis (NCA) of PK parameters is standard for Phase 1 clinical trials.

